11.5 Data and Safety Monitoring Committee Oversight

A Data and Safety Monitoring Committee will oversee the conduct of the study. The Committee consists of four members from outside of SWOG, three SWOG members, three non-voting representatives from the National Cancer Institute (NCI), and the Group Statistician (non-voting). The members of this Committee will receive confidential reports every six months from the SWOG Statistical Center, and will meet at the Group's bi-

annual meetings as necessary. The Committee will be responsible for decisions regarding possible termination and/or early reporting of the study.

12.0 DISCIPLINE REVIEW

12.1 Surgeon Credentialing

Each surgeon must be pre-approved and credentialed to participate in this study. Credentialing will be performed by the Study Chairs and will include:

- a. Completion of accredited urologic residency training (for all participating surgeons);
- b. Cumulative number of radical cystectomies over past 3 years ≥ 50 ;
- c. Number of radical cystectomies performed at your hospital(s) (not necessarily by one surgeon) $> 30/\text{year}$;
- d. De-identified operative and pathology reports from five recent radical cystectomies;
- e. Representative intra-operative photos (or edited video) demonstrating complete extended pelvic and iliac lymphadenectomy. Minimum photos required are right and left pelvic and extended LND if this was performed showing right and left CI, pre-sacral and proximal limit of dissection.

A completed **S1011** Surgeon Credentialing Checklist (available on the **S1011** protocol abstract page on <http://swog.org>) plus operative reports, pathology reports, and photo documentation must be submitted electronically to the SWOG Genitourinary Protocol Coordinator at [contact] for distribution to the Study Chairs. Within two weeks of submission of all credentialing information, the SWOG Operations Office or Study Chair will notify the surgeon when approved for participation. No registration will be accepted until the surgeon is credentialed. Credentialing may be subject to review at time of audit. See also Section 14.0 for on-study data submission requirements.

12.2 Surgery Review

- a. All surgeries performed as part of this study will undergo a central surgical review. The goal of this review is to verify that the lymph node dissection was done according to the assigned randomization and the criteria specified in Section 7.0 of the protocol.
- b. The following are required to be submitted within 14 days of surgery to the SWOG Data Operations Center in Seattle (see [Section 14.4b](#)):
 1. **S1011** Intra-Op Surgical Assessment Form Standard versus Extended LND;
 2. Digital image(s) of intra-operative photo(s) showing extent of node dissection;
 3. Copy of the operative report(s);

4. Copy of corresponding pathology report(s).

The **S1011** Urology Study Chairs will review all these data within 7 days of receipt and interact with the surgeons at each site to provide feedback in order to ensure the consistency of the extent of node dissection in the two arms.

Independent oversight will be provided by the SWOG Surgery Quality Committee who will review these data at least annually and make recommendations for improvement in monitoring and data collection as needed.

13.0 REGISTRATION GUIDELINES

NOTE: Participation in this study is limited to pre-approved, credentialed surgeons. The SWOG Operations Office or Study Chair will notify each surgeon when approved for participation. The registering physician must be the pre-approved, credentialed surgeon intended to perform the assigned procedure.

13.1 Registration Timing

Patients must be registered prior to surgery (no more than 28 calendar days prior to planned surgery).

13.2 Investigator/Site Registration

This study is supported by the NCI Cancer Trials Support Unit (CTSU).

Prior to the recruitment of a patient for this study, investigators must be registered members of a Cooperative Group. Each investigator must have an NCI investigator number and must maintain an "active" investigator registration status through the annual submission of a complete investigator registration packet (FDA Form 1572 with original signature, current CV, Supplemental Investigator Data Form with signature and Financial Disclosure Form with original signature) to the Pharmaceutical Management Branch, CTEP, DCTD, NCI. These forms are available on the CTSU Web site (enter credentials at <https://www.ctsu.org>; then click on the Register tab) or by calling the PMB at [name] Monday through Friday between 8:30 a.m. and 4:30 p.m. Eastern time.

Each investigator or group of investigators at a clinic site must obtain IRB approval for this protocol and submit IRB approval and supporting documentation to the CTSU Regulatory Office before they can enroll patients. Study centers can check the status of their registration packets by querying the Regulatory Support System (RSS) site registration status page of the CTSU member web site by entering credentials at <https://www.ctsu.org>.

Requirements for site registration:

- CTSU IRB Certification
- CTSU IRB/Regulatory Approval Transmittal Sheet

13.3 OPEN Registration Requirements

The individual registering the patient must have completed the appropriate SWOG Registration Worksheet. The completed form must be referred to during the registration but should not be submitted as part of the patient data.

Oncology Patient Enrollment Network (OPEN) will also ask additional questions that are not present on the SWOG Registration Worksheet. The individual registering the patient must be prepared to provide answers to the following questions:

- a. Institution CTEP ID
- b. Protocol Number
- c. Registration Step
- d. Treating Investigator
- e. Cooperative Group Credit
- f. Credit Investigator
- g. Patient Initials
- h. Patient's Date of Birth
- i. Patient SSN (SSN is desired, but optional. Do not enter invalid numbers.)
- j. Country of Residence
- k. ZIP Code
- l. Gender (select one):
 - Female Gender
 - Male Gender
- m. Ethnicity (select one):
 - Hispanic or Latino
 - Not Hispanic or Latino
 - Unknown
- n. Method of Payment (select one):
 - Private Insurance
 - Medicare
 - Medicare and Private Insurance
 - Medicaid
 - Medicaid and Medicare
 - Military or Veterans Sponsored NOS
 - Military Sponsored (Including Champus & Tricare)
 - Veterans Sponsored
 - Self-Pay (No Insurance)
 - No Means of Payment (No Insurance)
 - Other
 - Unknown
- o. Race (select all that apply):
 - American Indian or Alaska Native
 - Asian
 - Black or African American
 - Native Hawaiian or other Pacific Islander
 - White Unknown

13.4 Registration Procedures

- a. All site staff will use OPEN to enroll patients to this study. OPEN is integrated with the CTSU Enterprise System for regulatory and roster data and, upon enrollment, initializes the patient in the Rave database. OPEN can be accessed

at <https://open.ctsu.org>, from the OPEN tab on the CTSU members' side of the website at <https://www.ctsu.org>, or from the OPEN Patient Registration link on the SWOG CRA Workbench.

- b. Prior to accessing OPEN site staff should verify the following:
 - All eligibility criteria have been met within the protocol stated timeframes. Site staff should refer to [Section 5.0](#) to verify eligibility.
 - All patients have signed an appropriate consent form and HIPAA authorization form (if applicable).
 - The study site is listed as "approved" in the CTSU RSS.
- c. Access requirements for OPEN:
 - Site staff will need to be registered with CTEP and have a valid and active CTEP-IAM account. This is the same account (user ID and password) used for the CTSU members' web site.
 - To perform registrations, the site user must have been assigned the 'Registrar' role on the SWOG or CTSU roster:
 1. If you are a SWOG member, to perform registrations on SWOG protocols you must have an equivalent 'Registrar' role on the SWOG roster. Role assignments are handled through SWOG.
 2. If you are not a SWOG member, to perform registrations on SWOG protocols you must have the role of Registrar on the CTSU roster. Site and/or Data Administrators can manage CTSU roster roles via the new Site Roles maintenance feature under RSS on the CTSU members' web site. This will allow them to assign staff the "Registrar" role.

Note: The OPEN system will provide the site with a printable confirmation of registration and treatment information. Please print this confirmation for your records.

- d. Further instructional information is provided on the OPEN tab of the CTSU members' side of the CTSU website at <https://www.ctsu.org> or at <https://open.ctsu.org>. For any additional questions contact the CTSU Help Desk at [name] or [contact].

13.5 Exceptions to SWOG registration policies will not be permitted.

- a. Patients must meet all eligibility requirements.
- b. Institutions must be identified as approved for registration.
- c. Registrations may not be cancelled.
- d. Late registrations (after initiation of treatment) will not be accepted.

14.0 DATA SUBMISSION SCHEDULE

14.1 Data Submission Requirement

Data must be submitted according to the protocol requirements for **ALL** patients registered, whether or not assigned treatment is administered, including patients deemed to be ineligible. Patients for whom documentation is inadequate to determine eligibility will generally be deemed ineligible.

14.2 Master Forms

Master forms can be found on the protocol abstract page on the SWOG website (www.swog.org) and (with the exception of the sample consent form and the Registration Worksheet) must be submitted on-line via the Web; see below for details.

14.3 Data Submission Procedures

Institutions must submit on-study data electronically via the Web by using the SWOG CRA Workbench and follow-up data through the Medidata Rave® clinical data management system.

- a. To access the CRA Workbench **for on-study data**, go to the SWOG Web site (<http://swog.org>) and logon to the Members Area. After you have logged on, click on the *CRA Workbench* link to access the home page for CRA Workbench website. Next, click on the *Pre-Rave Data Submission* link and follow the instructions.

To submit data via the web the following must be done (in order):

1. You are entered into the SWOG Roster and issued a SWOG Roster ID Number,
2. You are associated as an investigator or CRA/RN at the institution where the patient is being treated or followed, and
3. You have an active CTEP-IAM account (check at <https://ctepcore.nci.nih.gov/iam/index.jsp>)

For assistance with points 1 and 2 call the Operations Office at [name]. For other difficulties with the CRA Workbench, please email [contact].

- b. To submit **follow-up data**, access to the trial in Medidata Rave® is granted through the iMedidata application to all persons with the appropriate roles assigned in Regulatory Support System (RSS). To access Rave via iMedidata, you must have an active CTEP-IAM account (check at <https://ctepcore.nci.nih.gov/iam/index.jsp>) and the appropriate Rave role (Rave CRA, Read-Only, Site Investigator) on either the LPO or participating organization roster at the enrolling site.

All users at sites that were approved for registrations in RSS will be sent a study invitation e-mail from iMedidata. To accept the invitation, site users must log into the Select Login (<https://login.imedidata.com/selectlogin>) using their CTEP-IAM user name and password, and click on the “accept” link in the upper right-corner of the iMedidata page. Please note, site users will not be able to access the study in Rave until all required Medidata and study specific trainings are completed. Trainings will be in the form of electronic learnings (eLearnings), and

can be accessed by clicking on the link in the upper right pane of the iMedidata screen.

Users that have not previously activated their iMedidata/Rave account at the time of initial registration approval for the study in RSS will also receive a separate invitation from iMedidata to activate their account. Account activation instructions are located on the CTSU website, Rave tab under the Rave resource materials (Medidata Account Activation and Study Invitation Acceptance). Additional information on iMedidata/Rave is available on the CTSU members' website under the Rave tab at www.ctsu.org/RAVE/ or by contacting the CTSU help Desk at [name] or by e-mail at [contact].

You may also access Rave® via the SWOG CRA Workbench on the SWOG website (www.swog.org) by clicking the link for Rave Data Submission.

- c. If you need to submit data that are not available for online data submission, the only alternative is via facsimile. Should the need for this occur, institutions may submit data via facsimile to [name] or [name] locally. Please do not use a cover sheet for faxed data. Please make sure that each page of all faxed data include the SWOG patient number, study ID and patient initials

14.4 Data Submission Overview and Timepoints

- a. WITHIN 7 DAYS OF STEP 1, REGISTRATION:

Submit the following:

S1011 Prestudy Form

Operative Report from TURBT

Pathology Report from TURBT

Radiology reports from cross-sectional imaging performed to determine the pre-REG clinical T stage, e.g. CT, MRI, or PET/CT.

- b. WITHIN 14 DAYS OF SURGERY, FOR ALL PATIENTS RECEIVING ON-STUDY SURGERY:

Submit copies of the following:

S1011 Intra-Op Surgical Assessment Form Standard Versus Extended LND

Intra-Op Photos

(Note: The Photo Upload Form is located in the data submission section of the SWOG CRA Workbench in the **S1011** Reg 2 folder under the 'Follow Up' tab. Photos should be obtained after the randomization and surgical assessment).

Operative Report from cystectomy

Pathology Report from cystectomy

- c. IF PATIENT CONSENTED, WITHIN 28 DAYS OF RANDOMIZATION:

Submit specimens as outlined in [Section 15.0](#).

- d. IF PATIENT NOT ELIGIBLE OR NOT CONTINUING TO STEP 2 RANDOMIZATION, WITHIN 14 DAYS AFTER GOING OFF STUDY:

S1011 Pre-Randomization Off Study Form

S1011 Intra-Op Surgical Assessment Form Standard Versus Extended LND
(Note: No Intra-Op photos are required for patients not going on to Step 2, Randomization)

e. WITHIN 7 DAYS FROM HOSPITAL DISCHARGE:

S1011 Surgeon's Post-Op Data Form Standard Versus Extended LND

S1011 Adverse Event Form

f. WITHIN 90 DAYS POST-SURGERY

S1011 Surgeon's 90-Day Assessment Form Standard Versus Extended LND

S1011 Adverse Event Form

g. AFTER SURGERY, EVERY THREE MONTHS FOR YEAR ONE; EVERY SIX MONTHS FOR YEARS TWO AND THREE; AND ANNUALLY UNTIL SIX YEARS AFTER RANDOMIZATION OR UNTIL DEATH:

Submit copies of the **S1011** Follow Up Form
(via the Medidata Rave® clinical data management system)

h. WITHIN 4 WEEKS OF KNOWLEDGE OF DEATH:

Submit the Notice of Death **and a final S1011** Follow Up Form.
(via the Medidata Rave® clinical data management system)

15.0 SPECIAL INSTRUCTIONS

Specimens for banking and translational medicine studies (submitted to the SWOG Specimen Repository – Solid Tissue, Myeloma and Lymphoma Division, Lab #201) are optional for the patient.

Sites must seek additional patient consent for the future use of paraffin embedded tissue (or slides). If patient consents, specimens must be submitted as described below. Specimens will be banked for future use including exploration of the role of epithelial-to-mesenchymal transition in bladder cancer metastasis (see Appendix 18.2 for a description of methods). The translational medicine studies will be performed once funding is obtained.

15.1 Specimen Submission Timepoints

With patient's consent, specimens must be submitted at the following times (see [Section 9.0](#)):

Within 28 days of randomization, submit:

- a. Two paraffin embedded blocks (preferred) or 10 unstained slides from the primary tumor (allowed, if the primary tumor blocks will not be released) AND a copy of the pathology report
- b. Eight unstained, 4-micrometer (μ m), formalin-fixed, paraffin-embedded (FFPE) sections from the "left pelvic" and "right pelvic" lymph node packets

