5.6 Disease-related Criteria (Step 2)

- a. Patients must not have intra-operative evidence of pelvic lymph node involvement (confirmed by frozen section) at or above the bifurcation of the common iliac vessels in any of the extended template. **Rationale:** Failure to excise lymph nodes with known cancer involvement would be a substantial deviation from standard of care or may be a cause for abandoning the operation in favor of systemic chemotherapy.
- b. Patients must not have intra-operative evidence of T4b disease.

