7.4 Submission of Lymph Nodes

At a minimum the standard pelvic lymph node dissection will be submitted to the institutional pathologist for routine histology in two separate packets labeled left and right pelvic. The extended pelvic lymph node will be submitted in a minimum of 3 packets labeled left and right common iliac (including the tissue dissected from the fossa or Marseilles - also referred to as pre-sciatic) and pre-sacral. If the nodes are dissected from the bifurcation of the aorta proximally then these will be submitted as a separate packet(s). All of these regions may be submitted in smaller packets (e.g. external iliac, obturator, internal iliac) at the surgeon's preference. The [S1011](#) Intra-Op Surgical Assessment Form describing the node packet submission to pathology must be completed and submitted to the Data Operations Center in Seattle per [Section 14.4b](#).

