The 'seed-and-soil' hypothesis was proposed by Paget in 1889, and suggests that the biological characteristics of certain tissues may foster invasion and growth of metastases. (23) Identification of these susceptible areas, termed pre-metastatic niches, has numerous possible clinical applications. For instance, patients with more abundant niches may have increased metastatic potential – niche prevalence could therefore serve as a personalized supplement to current prognostic models. (24)

In bladder cancer, we have generated preliminary data suggesting that the pre-metastatic niche may be marked by neutrophils (i.e., CD15⁺ cells). Specifically, we have assessed benign nodal tissue derived from 20 patients with muscle-invasive bladder cancer. Through an IRB-approved protocol (COH IRB 11210), benign lymph node tissue collected at the time of cystectomy from a cohort of 20 patients was obtained. These patients had (1) a pathologically verified diagnosis of muscle invasive disease prior to cystectomy, (2) pT2a-T4N0 disease determined at the time of cystectomy, (3) no radiographic evidence of metastasis prior to cystectomy, and (4) available paraffin-embedded sections

encompassing both primary tumor and benign lymph nodes. From these patients, 4 μ m sections of benign lymph node tissue were stained with monoclonal antibodies directed at VEGFR1 (ImClone Systems) and CD15 (a human neutrophil marker; Abcam). Stained sections for pSTAT3 (Santa Cruz Biotechnology) were performed, since recent data suggest the potential role of phosphorylated Signal transducer and activator of transcription 3 (pSTAT3) in mediating neutrophil recruitment to pre-metastatic sites. (25) Co-localization of VEGFR1 and CD68⁺ macrophages was observed, and sections were stained with a monoclonal antibody directed at CD68 (Signet). Image Pro Plus software was used to count positive cells and an average count across the 8-100x fields was used for statistical analyses. The median age of this cohort was 70 (range, 40-86), and the cohort included a relatively balanced number of patients with clinical stage 2 and 3 disease (11 patients and 9 patients, respectively). Only 1 patient had received neoadjuvant chemotherapy in this cohort, and 2 patients had received adjuvant treatment (all 3 patients received cisplatin/gemcitabine as their cytotoxic regimen).

[figure not shown]

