Several correlative studies have been built into the original protocol. The statistical considerations for the current study are slightly different, as we plan to incorporate a testing and validation cohort. We expect that 395 patients will have usable lymph node samples as specified in the protocol (assuming that tissue is available for 70% of study participants). The testing cohort will be comprised of the first half of these patients, or approximately 200 patients, and the results from the second 200 patients will be used for validating the results. On a case by case basis, some patients who are found to be ineligible for the clinical trial due to reasons other than pathology may be used for these analyses.

The underlying hypothesis for the correlative studies associated with this aim is that biomarker expression levels (i.e., (CD15, pSTAT3, VEGFR1 and CD68 cell counts in the benign nodal tissue) may predict clinical outcome (i.e., DFS). For each biomarker, recursive partitioning will be used to determine the cutoff value of average cell count that maximally distinguishes DFS within the training cohort. These cutoffs will be examined in the validation cohort.

[Table 1](#) provides an estimate of the minimally detectable hazard ratio for DFS for those with an elevated biomarker expression level (i.e., high CD15

	Prevalence of "High" Biomarker Expression Level				
	10%	20%	30%	40%	50%
DFS HR	2.40	1.93	1.80	1.74	1.73

Table 1. Minimally detectable hazard ratio (HR) for DFS for those with "high" biomarker expression versus those with "low" biomarker expression. Assuming 80% statistical power, 2-sided alpha of 0.05, and 200 patients in the training set (same power for the 200 patients in the validation set).

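### The niche markers are defined on benign nodal tissue, but the collection rule requires no tumor-free node and the cutoff analysis does not account for pN status

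*Combined protocol and SAP*

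**What the plan says.** - **What is measured.** The statistical plan in Appendix 18.2b states its hypothesis for "CD15, pSTAT3, VEGFR1 and CD68 cell counts in the benign nodal tissue". The 20-patient pilot behind it was limited to "pT2a-T4N0 disease determined at the time of cystectomy".
- **What is collected.** Section 15.1b requests eight unstained "formalin-fixed, paraffin-embedded (FFPE) sections from the 'left pelvic' and 'right pelvic' lymph node packets", and the Section 9.0 calendar repeats the request. Neither mentions a tumor-free node. Under Section 7.4 the standard dissection goes to pathology as at least "two separate packets labeled left and right pelvic".
- **Who is eligible.** Section 5.6a excludes frozen-section-confirmed disease only "at or above the bifurcation of the common iliac vessels in any of the extended template". Section 5.2c likewise concerns nodal disease proximal to that bifurcation. Section 7.3 makes a recommendation for N+ patients, so they are expected on study.
- **How many, and how analyzed.** The appendix states: "We expect that 395 patients will have usable lymph node samples as specified in the protocol", at 70% tissue availability. The first half of these patients sets each marker's cutoff by recursive partitioning on DFS, and the second half validates it. A later AUC comparison uses a clinical model that includes pathologic stage but does not name pN.

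**The concern.** A neutrophil or macrophage count in a node that already holds metastasis is not a pre-metastatic measurement. The pelvic packets hold the external iliac, internal iliac and obturator nodes, and Section 4.0 places N1 and N2 disease at those sites. Appendix 18.2b passes from background to statistical plan with no assay-methods section, so nothing there says how a positive packet is handled.

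Nodal status is strongly related to DFS. A search for the cutoff that best separates DFS can settle on one that detects metastasis, if counts differ in metastatic tissue. The validation half is collected under the same rule, so it would tend to reproduce the artefact. At stake is the meaning of a positive result for Objective 1.3b: a new prognostic marker, or nodal stage measured another way.

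**Working it through.** **1. The plan's own figure.** 0.70 × 564 = 394.8, which reproduces the stated 395. It is 70% of all eligible patients, with nothing removed for node-positive disease.

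**2. Node-positive patients among them.** Applying the 14% to 40% in Section 2.0: 0.14 × 395 = 55 and 0.40 × 395 = 158, or 28 to 80 of each 200. This assumes that the published rates carry over to this trial and to the patients who consent to banking.

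**3. Strength of pN.** Section 2.0, Table 1 has five series with 5-year DFS for both nodal groups. With exponential DFS, HR = ln(S pos) / ln(S neg).

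| Series size | N neg | N pos | HR |
|---|---|---|---|
| 1054 | 78% | 35% | 4.23 |
| 788 | 75% | 21% | 5.42 |
| 888 | 80% | 35% | 4.70 |
| 2720 | 62% | 27% | 2.74 |
| 432 | 72% | 29% | 3.77 |

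All exceed the detectable hazard ratios in the appendix's own Table 1: 2.40, 1.93, 1.80, 1.74 and 1.73 at 10% to 50% prevalence. They bound the artefact from above: a marker reaches them only if it reads high in every pN+ patient and in no pN0 patient.

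**4. A marker with no effect of its own.** Simulation of 60,000 patients per row. DFS is exponential with 5-year values of 72% (pN0) and 30% (pN+), chosen within the ranges above. Censoring is uniform over 3 to 8 years, matching 5 years of accrual plus 3 of follow-up. The marker reads high if a pN+ patient's section contains metastasis (share t), or at random in any patient (rate r). The documents give neither t nor r, nor do they say that counts rise in metastatic tissue; these are assumptions. The HR is from a Cox model, high versus low, with a Monte Carlo standard error of about 2%.

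| pN+ | t | r | Prevalence of high | HR | HR with pN in model | Stated detectable HR at adjacent prevalences |
|---|---|---|---|---|---|---|
| 27% | 50% | 0 | 13.5% | 2.81 | 0.99 | 2.40 (10%), 1.93 (20%) |
| 27% | 50% | 10% | 22% | 1.90 | 0.98 | 1.93 (20%), 1.80 (30%) |
| 27% | 25% | 10% | 16% | 1.52 | 0.99 | 2.40, 1.93 |
| 14% | 25% | 10% | 13% | 1.41 | 1.01 | 2.40, 1.93 |
| 27% | 25% | 20% | 25% | 1.29 | 0.98 | 1.93, 1.80 |
| 14% | 25% | 20% | 23% | 1.20 | 0.98 | 1.93, 1.80 |

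The first row is above the detectable values, the second is about equal to them, and the other four are below. Adding pN to the model returns the hazard ratio to about 1 in every row.

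**5. Cost of a pN0-only analysis.** 395 × 0.86 = 340 and 395 × 0.60 = 237, so 170 or 118 per half instead of 200. At 20% prevalence (high-group median 3 years, 80% power, two-sided 0.05), the detectable HR by Schoenfeld's formula goes from 2.00 to 2.15 or 2.63. With variance 1/d₁ + 1/d₂ (d = events per marker group) it goes from 1.85 to 1.96 or 2.26. The stated 1.93 lies between the two starting values; no single approximation tried reproduces the appendix's whole row. The rise is about 0.1 to 0.6.

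**The case against.** The strongest reply is that the restriction already exists where it matters. The measured quantity is defined as benign tissue, the samples are called usable, and calendar footnote e has specimens collected after final pathology, so nodal status is known when a block is chosen. Section 15.2 also places the detailed submission instructions on a webpage outside the documents, which may contain a tumor-free rule. All of this shows intent and feasibility. It does not put the condition into Section 15.1b or the calendar, and it does not say what happens to a pN+ packet.

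Second, the AUC comparison asks what the markers add to a model with pathologic stage. If that term includes pN, a marker that only stands in for pN should add little. This is a real partial safeguard, but pN is not named, and neither the cutoff search nor the single-marker comparison is described as adjusted.

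Three stronger readings are tempting and should not be adopted:

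- A reader might infer that eight sections equal four markers on two sides, leaving none to confirm that tissue is benign. No document allocates slides to stains, eight may mean per packet, and pathology reports are submitted.
- A reader might infer that a null marker would look positive. The table above shows only that it could, under some inputs.
- A reader might infer that cutoffs must be derived in pN0 patients alone. Objective 1.3b covers muscle-invasive disease, that restriction could cost up to 40% of samples, and adjustment for pN removed the artefact in every scenario without losing patients.

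**Conclusion.** The point holds as a mismatch between the tissue on which the markers are defined and the tissue requested, together with a cutoff analysis that does not account for pN. About 55 to 158 of the 395 samples may come from pN+ patients. How many of those sections contain tumor cannot be derived from the documents.

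The spurious hazard ratio was roughly 1.2 to 2.8 under the inputs tried. It rests on exponential DFS, on the historical DFS by nodal status, and on counts being higher where metastasis is present. Its size is uncertain; it reached or passed the stated detectable values in two of six scenarios.

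The change should be made, but its weight is limited. The niche study uses optional banked tissue and awaits funding (Section 15.0). No primary or secondary endpoint depends on it.

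**What to change.** 1. **Collection (Section 15.1b and calendar).** Require sections from a node that final pathology reported tumor-free on each side. Mark a side not evaluable if it has no such node.
2. **Tissue already banked.** The document is marked closed effective 04/15/2017, so this step probably matters most. Use the cystectomy pathology reports submitted under Section 14.4b to exclude or flag sections from positive nodes.
3. **Analysis (Appendix 18.2b).** Name pN status in the clinical model. Stratify or adjust for pN when deriving cutoffs and when validating them. Add a pN0-only analysis as a sensitivity analysis, which matches the pilot population.
4. **Sample size.** Describe 395 as an upper bound on evaluable samples, and present the appendix's detectable hazard ratios as best-case values.

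The cost is a sentence in the specimen section, a review of reports already held, and analysis wording. Somewhat fewer samples will be evaluable and detectable hazard ratios will be slightly larger. Patients with positive nodes may still have a negative node on each side, so the loss should be smaller than under pN0 restriction, but the documents do not allow it to be calculated.
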